### 14.0 BIostatISTICS

The primary comparison will be the difference in pain relief recorded as the "area under the curve" (AUC) between the initial 2 mg morphine dose and the study drug. AUC will be estimated by plotting % of pain relief over the time (see Appendix 6).

Time (t) for each AUC will include:

For area A:

- t0, time of the first request for the analgesia and opened administration of 2 mg morphine;
- t2, 3, ..., time of assessments 10 minutes apart
- tn, time of the second request for analgesic medication and study drug administration.

For area B:

- t0 time of the second request for analgesic medication and study drug administration;
- t2, 3, ..., time of assessments 10 minutes apart;
- tn, time of the third request for analgesic medication and completion of the study.

Pain relief at the time of the request for pain medication will be considered baseline and each patient will serve as his own control. Should the pain relief score at the time of the second pain medication administration be reported higher than the baseline, projected AUC will be used, extending it to the baseline.

AUC for 2 mg morphine (area B1) and AUC for a combination of 1 mg morphine and 1 mg methadone (area B2) will be compared to the AUC for open label 2 mg morphine (area A).

**Memorial Sloan-Kettering Cancer Center  
IRB Protocol**

**IRB#: 05-025A(7)**

If the true difference between mean ratio B/A for morphine plus methadone vs morphine alone is .68 times the within-group standard deviation, then with 35 patients completing the study per arm there would be an 80% chance of a significant comparison with a two-sided t-test at  $p < 0.05$ .

The main analysis will be the analysis of covariance, using baseline pain as a covariate, and analyze time-to-first-rescue (the time from stopping PCA to first request for analgesic medication), and changes in pain intensity as secondary outcomes. We will also collect the information about the total dose of morphine received while on IV PCA and the dose of morphine received during the last hour before stopping the PCA and the time from stopping PCA to first request for analgesic medication to stratify subjects during analysis.

We are planning to review the data after 10 cases and may need to adjust the dose of morphine as well as morphine and methadone accordingly, by doubling the dosage. With the change of the dose, a new patient accrual will be started. The data for the initial opioid dose will be analyzed separately.

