**IRB#: 05-025A(7)**

- Pain relief scores on a 0-100% scale
- Pain intensity scores on a 0-10, 11 point, verbal scale
- Respiratory rate
- Side effects from the pain medication and their severity rated by the patient on a 0-3 scale (none, mild, moderate, severe)
- Time to the second request for the pain medication
- Global assessment. The patients will be asked: "How effective was the medication in relieving your pain?" The patient will choose among: 1) not effective 2) slightly effective 3) moderately effective 4) very effective 5) extremely effective.

Immediately before administration of the study drug, i.e. morphine 2 mg IV or morphine 1 mg with methadone 1 mg IV, every 10 minutes and at the time of the third request for analgesia, we will record (See Appendix 5):

- Pain relief scores on a 0-100% scale
- Pain intensity scores on a 0-10, 11 point, verbal scale
- Respiratory rate
- Side effects from the pain medication and their severity rated by the patient on a 0-3 scale (none, mild, moderate, severe)
- Global assessment. The patients will be asked: "How effective was the medication in relieving your pain?" The patient will choose among: 1) not effective 2) slightly effective 3) moderately effective 4) very effective 5) extremely effective.
- Time to the third request for the pain medication (upon which the study is completed)

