## **11.0 TOXICITIES/SIDE EFFECTS**

Methadone has been in widespread use for decades and has been studied extensively. The most frequently observed side effects include sedation, nausea, vomiting, constipation, confusion and hallucinations, which are more pronounced in ambulatory patients and less common at lower doses. Methadone accumulation is not a concern in the current study because of the single dose design. Methadone-related side effects are easily reversed by naloxone.

Morphine is the standard opioid used for post-operative care. Subjects will receive a dose of 2 mg morphine intravenously, immediately when they request the analgesia medication. This dose may be slightly lower or higher than the dose of morphine received via continuous infusion previously. This may result in temporary improvement or worsening of pain control. The most serious side effect is respiratory depression, particularly with rapid administration. Low doses of intravenous morphine have little effect on cardio-vascular stability. High dose morphine may cause sympathetic over activity, dysphoria and convulsions. Nausea, vomiting, constipation, headache, anxiety, pruritus and urinary retention may be seen at lower doses and easily reversed by naloxone.

Given the relatively small amount of opioid used in the study drug (morphine 1 mg plus methadone 1 mg), we do not expect any side effects. However, due to the potential for synergism and, therefore, potentiation of the effect, we will closely monitor the patient for the presence of side effects (see Section 10, Evaluation During Treatment). NCI Common Toxicity Criteria 3.0 will be used to categorize and grade toxicity. Toxicities of grade 2 or less will be treated symptomatically. For patients with grade 3 or 4 toxicities, morphine and methadone will be stopped and an appropriate alternative analgesic regimen will be started.

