## 12.0 CRITERIA FOR THERAPEUTIC RESPONSE/OUTCOME ASSESSMENT

Primary endpoint will be the difference between the pain relief offered by a combination of 1 mg morphine with 1 mg methadone intravenously (IV) and 2 mg of IV morphine alone. The outcome measure will be pain relief evaluated as the area under the curve (AUC) (Houde). AUC is the area under the drug level-time curve made by plotting pain relief (0-100%) to the time to the next request for pain medication (see Appendix 6).

Time (t) for each AUC will include:

For area A:

- t0, time of the first request for the analgesia and open administration of 2 mg morphine;
- t2, 3, ..., n, time of assessments 10 minutes apart;
- tn, time of the second request for the analgesia and study drug administration.

For area B:

- t0, time of the second request for the analgesia and study drug administration;
- t2, 3, ..., n, time of assessments 10 minutes apart;
- tn, time of the third request for the analgesia and completion of the study.

Effectiveness of the study drug will be estimated by comparing it to the open label 2 mg morphine IV. Ratio of pain relief offered by a combination of 1 mg morphine and 1 mg methadone IV to the analgesia provided by open label 2 mg morphine IV will be compared to the ratio of pain relief offered by 2mg morphine given in the blind fashion to the open label 2 mg morphine IV (see Appendix 6).

Hypothesis: AUC B2/A ratio is higher than the AUC B1/A ratio.

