**At the time of the first request for analgesic medication**

1. On a scale of 0-100%, where 0 is no pain relief and 100% is complete pain relief, how would you rate your pain relief right now?
2. On a scale of 0-10, where 0 is no pain and 10 is the worse pain you can imagine, how would you rate the intensity of your pain right now?
3. Respirations per minute: \_\_\_\_\_
4. Side effects reported by the patient: \_\_\_\_\_

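### The primary hypothesis and power rest on the per-patient ratio B/A, and no visible rule covers a zero or very small A

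*Combined protocol and SAP*

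**What the plan says.** Section 12.0 puts the hypothesis on a ratio: "Hypothesis: AUC B2/A ratio is higher than the AUC B1/A ratio". Section 14.0 powers the trial on the same quantity ("If the true difference between mean ratio B/A for morphine plus methadone vs morphine alone is .68 times the within-group standard deviation"), with 35 completers per arm, 80% power and a two-sided t-test at 0.05. It then adds: "The main analysis will be the analysis of covariance, using baseline pain as a covariate". The outcome of that ANCOVA is not named. B/A can be inferred, but the opening sentence of Section 14.0 speaks of a difference between the initial dose and the study drug.

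Four provisions bear on how small A can be:

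- **Scale.** Section 10.0 lists "Pain relief scores on a 0-100% scale", and the Appendix 4 form explains the range as "where 0 is no pain relief and 100% is complete pain relief".
- **Timing.** Section 9.0 gives the study drug at once on the second request and sets no minimum interval.
- **Removal.** Section 13.0 removes patients who make no request within 4 hours of the open-label dose. It has no counterpart for patients with little or no relief.
- **Projection.** Section 14.0 extends the curve only when relief at the second dose is still above baseline.

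**The concern.** A's only stated role is as a divisor. If a patient reports no gain from the open-label dose, A can be zero and B/A does not exist. The trial must then drop or impute that patient in its primary analysis, by a rule chosen after the data are seen. If A is small but not zero and B is ordinary, one patient can set the arm mean and inflate its standard deviation.

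The power statement inherits the problem. An effect of 0.68 SD is expressed in units of a ratio whose SD is not given and can be driven by a few small divisors. The documents therefore do not show what difference in analgesia the trial is sized to detect.

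**Working it through.** **Stated power.** Inputs from Section 14.0: d = 0.68, 35 per arm, two-sided 0.05. Noncentrality = 0.68 × √(35/2) = 2.845 on 68 degrees of freedom, which gives power 0.8007. The 80% reproduces.

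**Undefined ratios.** If a proportion p of patients has A = 0, the chance of at least one undefined ratio among 70 is 1 − (1 − p)^70. For p = 0.5%, 1% and 2% (assumed) this is 30%, 51% and 76%.

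**One small divisor.** Suppose the area is measured above baseline. Relief rises 10 points at 10 minutes and is back at baseline, with a new request, at 20 minutes. By trapezoids, A = 10 × (0 + 10)/2 + 10 × (10 + 0)/2 = 100 %-min. With B = 2000 (assumed) the ratio is 20.

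Put this patient in an arm with 34 others whose ratios average 1.28. That mean follows from areas of log-SD 0.7 and A-B correlation 0.5 on the log scale, both assumed.

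- Arm mean: (34 × 1.28 + 20)/35 = 1.81, a shift of about 0.54, or 42% of the control mean.
- Typical arm SD: from 0.92 to 3.29.
- The same patient shifts the ANCOVA-adjusted difference in AUC_B by a median of 1.4% of the control mean (95th percentile 3.9%).

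**Meaning of 0.68 SD.** With log-SD from 0.4 to 1.0 and correlation from 0.3 to 0.8, all assumed, 0.68 SD of B/A equals 17.5% to 119% of the control mean ratio, before any near-zero A.

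**Power by simulation.** 35 per arm, lognormal areas with median 2000 %-min, 60% gain in B, log-scale correlation rho, baseline pain left out. All these values are assumptions, because the documents give no SDs, correlations or frequencies of small A. Repeat runs differ by 0.01 to 0.03.

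| Setting | Ratio t-test | Raw ANCOVA |
|---|---|---|
| log-SD 0.7, rho 0.5, no small areas | 0.69 | 0.78 |
| same, 3% of A at 100 | 0.18 | 0.76 |
| same, A and B both at 100 in 5% of patients | 0.68 | 0.76 |
| log-SD 1.0, rho 0.7, no small areas | 0.59 | 0.51 |
| log-SD 1.0, rho 0.8, no small areas | 0.80 | 0.64 |

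Rank ANCOVA reached 0.72 and 0.85 in the last two rows. With no true effect and 3% of A at 100, the ratio test rejected in 1.7% of trials and raw ANCOVA in 4.9%. The unprotected divisor therefore costs power and does not produce false positives.

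**Power on the new scale.** With AUC_A as covariate, the effect detectable with 80% power is 0.68 × √(1 − r²) SD of AUC_B, where r is the raw-scale correlation. This gives 0.65, 0.59 and 0.41 for r = 0.3, 0.5 and 0.8. The simulation's rho is on the log scale; at log-SD 0.7, rho 0.5 corresponds to r of about 0.44.

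**The case against.** A reader might infer that the protocol itself expects little or no relief from the open-label dose. The text does not support that.

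- Section 11.0 says "This may result in temporary improvement or worsening of pain control", but it is comparing the dose with the earlier infusion and names both directions.
- The Section 10.0 options beginning "1) not effective 2) slightly effective" are the lower end of a five-point scale.
- Section 14.0 says the team "may need to adjust the dose of morphine as well as morphine and methadone accordingly, by doubling the dosage" after 10 cases, but gives no reason. A change would start new accrual with separate analysis, which would partly contain a weak response.
- Section 5.0 gives morphine analgesia as lasting 3-4 hours, far longer than the 20 minutes of the worked example.

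This objection stands: a small A is possible, and its frequency is unknown.

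The worked example also needs the area to be measured above baseline. Section 14.0 calls relief at the request the baseline but does not say that it is subtracted. Without subtraction, a starting score of 30% (assumed) would give 30 × 20 + 100 = 700 %-min instead of 100.

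The collapse in power needs a small A beside an ordinary B. Control patients receive the same 2 mg morphine twice, so a poor response may well repeat, and then there is no collapse.

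ANCOVA is not uniformly better, as the last two rows of the table show. It also replaces a relative effect within each patient by an adjusted absolute difference, and SD units of AUC_B have no more clinical anchor than SD units of B/A. A prespecified rule for small A would close the narrow gap, but the result would still depend on the threshold chosen.

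Finally, the Appendix 6 drawing and a stretch of text between Sections 14.0 and 15.1 were not visible. No visible text points to a small-A rule in either.

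**Conclusion.** The concern holds in a limited form. Followed as written, the plan can give a primary result that is undefined for some patients or driven by one of them, and it states no rule for either case. This follows from the text and needs no simulation.

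The size is conditional. Power falls to 0.18 only under the assumed pattern of 3% of patients with a very small A and an ordinary B. It barely moves when both areas are low together. It would be wrong to conclude that the 80% figure is miscalculated, that the trial expects non-response, or that the ratio test is always the weaker choice. The change is worth making because ANCOVA is already the named main analysis and AUC_A comes from scores already recorded every 10 minutes.

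**What to change.** In Section 14.0:

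- Make the primary between-arm analysis an ANCOVA of AUC_B on randomised arm, with AUC_A and baseline pain as covariates. Report the adjusted difference with its 95% confidence interval, and also as a percentage of the control mean.
- Prespecify a rank-based ANCOVA (ranks of B on ranks of A) as the robustness check.
- Report B/A descriptively, with a stated rule for A = 0.
- State whether areas are measured above baseline, in the same way for A and B.
- Restate the power on the AUC_B scale: 35 per arm gives 80% for 0.65, 0.59 or 0.41 SD at an assumed raw-scale correlation of 0.3, 0.5 or 0.8. Say what difference in relief that represents.

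Reword the hypothesis in Section 12.0 to match, and bring the opening sentence of Section 14.0 into line with it.

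The cost is a few sentences and one degree of freedom, with no new data; 35 per arm can stay if the restated detectable effect is acceptable. The effect becomes an adjusted absolute difference instead of a ratio. With highly skewed, highly correlated, multiplicative data and no near-zero A, raw ANCOVA can have less power than the ratio test. The rank analysis did not lose in those settings.

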## 1.0 PROTOCOL SUMMARY AND/OR SCHEMA

Translational studies in analgesic pharmacology: analgesic synergy in clinical pain. A phase 2 study comparing a single dose of a 1:1 combination of methadone and morphine with morphine alone in patients with post-operative pain.

The objective of this proposal is to compare the analgesic effects of a combination of morphine and methadone with morphine alone to determine synergistic activity of mu opioid analgesics in humans.

This is a randomized, double blind, parallel arm study (See Appendix 1).

We will administer a single dose of 1 mg of IV methadone plus 1 mg of morphine or 2 mg of IV morphine to patients one day after retroperitoneal lymph node dissection. We are planning for 70 patients to complete the study, 35 in each group.

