All patients will receive Patient Controlled Analgesia (PCA) with IV morphine. The total amount of opioid available to patients will be equivalent to the standard amounts used after retroperitoneal lymph node dissection. Informed consent will be obtained from all patients pre-operatively. The PCA settings will start after the surgery at 1 mg/hour continuous infusion and 1mg every 10 minutes as needed. Clinician activated boluses (CAB) of morphine 5 mg IV will be available to the patient. The day after the surgery, the PCA will be stopped for the period of the study and we will ask the patient to request pain medication as soon as he feels at least moderate pain. During the period of the trial the physician will have no other clinical or other responsibilities. A physician will be available to monitor the time to the patient's request for pain medications, assess pain intensity and administer the drugs to replace the PCA promptly upon the patient's request. No more than 2 patients per the doctor per floor will be enrolled on the same day. When the patient requests pain medication, baseline pain intensity will be assessed and open label 2 mg of morphine administered. After administration of morphine the patient's pain relief, pain intensity, and side effects reported by the patient will be assessed every 10 minutes, and/or at the time the patient requests analgesia medication. In addition, respiratory rate will be recorded during these intervals. Immediately upon the second request for analgesia, the study drug in a double blind fashion (1 mg of IV methadone plus 1 mg of morphine or 2 mg of IV morphine), will be administered by the doctor. After administration of the study drug, pain relief, pain intensity, side effects reported by the patient and respiratory rate will be assessed every 10 minutes, and/or at the time the patient requests analgesia medication. Upon the third request for analgesia medication the study is completed, and the PCA will be restarted at the pre-study dose. We will also collect information about the total dose of morphine received while on IV PCA, the dose of morphine received during the last hour before stopping the PCA, and the time from stopping PCA to first request for analgesic medication.

**Memorial Sloan-Kettering Cancer Center  
IRB Protocol**

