**IRB#: 05-025A(7)**

Morphine 2 mg intravenously will be administered upon the first request for an analgesic medication. Upon the second request, depending on the randomization, the patient will receive morphine 2 mg intravenously or a combination of morphine 1 mg and methadone 1 mg intravenously. There will be no dose escalation.

	Upon the 1st Request for Analgesic Medication	Upon the 2nd Request for Analgesic Medication
Randomized to Group 1	morphine 2 mg	morphine 2 mg
Randomized to Group 2	morphine 2 mg	morphine 1 mg and methadone 1 mg

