## 8.0 PRETREATMENT EVALUATION

Demographic (age, ethnicity) and clinical data, including weight, height, past medical and surgical history, past treatment with opioids, concurrent drug therapies, drug-related side effects, and serum creatinine clearance within one month of surgery will be collected (See Appendix 3). We will also collect the data on the total dose of morphine received while on IV PCA, dose of morphine received during the last hour before stopping the PCA, and the time from stopping the PCA to first request for analgesic medication (See Appendix 4).

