**IRB#: 05-025A(7)**

continuous infusion and 1mg every 10 minutes as needed and titrated up as needed. CABs as needed will be available (See Appendix 1).

The day after the surgery the PCA will be stopped for the period of the study. We will ask the patient to request pain medication as soon as he feels moderate pain. The doctor will be present to monitor the time of the patient's request, assess pain intensity and administer drugs to replace the PCA promptly upon the patient's request. If two hours pass before a first request for pain medication is made, the patient will be removed from the protocol. Not more than two patients per doctor per floor will be enrolled on the same day. During the period of the trial, the doctor will have no clinical or other responsibilities.

1. When the patient requests pain medication, baseline pain intensity will be assessed and open label 2 mg of morphine IV administered. After administration of morphine, the patient's pain relief, pain intensity, respiratory rate, and side effects reported by the patient will be assessed every 10 minutes, and at the time of the second request for analgesia medication. If four hours pass before a second request for pain medication is made, the patient will be removed from the protocol.

2. Immediately upon a second request for analgesia, the study drug in a double blind fashion (1 mg of methadone IV plus 1 mg of morphine IV or 2 mg of morphine IV), will be administered by the doctor. After administration of the study drug, the patient's pain relief, pain intensity, respiratory rate, and side effects reported by the patient will be assessed every 10 minutes, and at the time of the third request for analgesia medication.

3. Upon a third request for analgesia medication or after four hours if no medication is requested, the study is completed and the PCA will be restarted at the pre-study dose. If four hours pass before a third request for pain medication is made, the patient will be removed from the protocol.

The total amount of opioid available to patients will be equivalent to the standard amounts used after retroperitoneal lymph node dissection.

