**1ST TREATMENT (MORPHINE ALONE)**

Time of the First Request for Analgesic Medication: \_\_\_\_\_

Time from Discontinuation of IV PCA to the First Request for Analgesic Medication: \_\_\_\_\_

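### The secondary outcome time-to-first-rescue ends before the blinded study drug is given, so it cannot measure a drug effect

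*Combined protocol and SAP*

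**What the plan says.** The order of events is the same in Sections 1.0, 4.2 and 9.0. The PCA is stopped, and the patient then makes up to three requests.

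- First request, both groups alike (Section 1.0): "Morphine 2 mg intravenously will be administered upon the first request for an analgesic medication".
- Second request (Section 1.0): "Immediately upon the second request for analgesia, the study drug in a double blind fashion" is given.
- Third request: the study ends.

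Section 14.0 plans to "analyze time-to-first-rescue (the time from stopping PCA to first request for analgesic medication), and changes in pain intensity as secondary outcomes". The parenthesis fixes the interval, so the label cannot be read as a time after study drug.

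Elsewhere the plan handles the same interval as baseline information. Section 8.0, on pretreatment evaluation, collects "and the time from stopping the PCA to first request for analgesic medication (See Appendix 4". Assessment Form 1 (Appendix 4) has the field "Time from Discontinuation of IV PCA to the First Request for Analgesic Medication" ahead of the open-label dose assessments. The sentence of Section 14.0 that follows the outcome definition lists this interval among the variables for stratifying the analysis.

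Time to the third request is recorded (Section 10.0 and Form 2, Appendix 5) and closes area B of the primary endpoint. Section 14.0 does not name it as a time outcome.

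On the four-hour limit after study drug, Section 9.0 states: "Upon a third request for analgesia medication or after four hours if no medication is requested, the study is completed". It then says such a patient is removed from the protocol; Sections 4.2 and 13.0 also have removal. Section 14.0 does not say whether this secondary outcome is analysed in all dosed patients or in completers only.

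**The concern.** A time-to-rescue outcome in an analgesic trial is meant to show how long the treatment lasts. This one stops the clock before the treatment is given, so a null result could be read as no effect on duration when the question was never tested.

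The second risk is less obvious. If the analysis is confined to completers, patients with no third request within four hours of study drug drop out. A longer-acting drug causes more such removals. If a patient's intervals are correlated, the patients lost are those with longer pre-dose intervals, and more of them go from the better arm. The combination arm could then look worse on a measure taken before it was given.

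Section 14.0 also uses one variable as both outcome and stratifier, and these roles do not fit together.

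**Working it through.** **1. Event order.** Write T1 for PCA stop to first request, T2 for first to second request (area A), and T3 for second to third request (area B).

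| Interval | Treatment at its start | Can the arms differ? |
|---|---|---|
| T1 | none; PCA stopped | no |
| T2 | open-label morphine 2 mg, both arms | no |
| T3 | blinded study drug | yes |

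The named outcome is T1. Section 15.2 generates the randomisation code after consent, which is pre-operative, so T1 falls after randomisation but before any difference in treatment. With blinding intact, the expected arm difference in T1 is zero in all dosed patients. The two-hour removal rule acts before study drug and does not alter this.

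**2. The plan's own power figure.** Inputs from Section 14.0: difference 0.68 SD, 35 completing per arm, two-sided 0.05.

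- Normal approximation: 0.68 × √(35/2) − 1.96 = 2.845 − 1.960 = 0.885; Φ(0.885) = 0.812.
- Exact noncentral t: 0.801.

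The stated 80% is reproduced. It concerns the B/A ratio and does not depend on the T1 definition. The plan gives no power for time-to-first-rescue.

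**3. T1 against T3 as the outcome.** Assumed: normal intervals, within-patient correlation 0.5, 35 per arm, 10,000 trials, two-sided t-test.

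| Drug effect on T3 (SD) | Rejection testing T1 | Rejection testing T3 |
|---|---|---|
| 0 | 4.9% | 4.9% |
| 0.68 | 5.3% | 80.5% |
| 1.5 | 4.9% | 100% |

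Testing T1 stays at about alpha however strong the drug is.

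**4. T1 as written, by analysis set.** Assumed: exponential times, T1 median 60 min (removed above 120 min), control T3 median 60 or 120 min, latent Gaussian correlation ρ between intervals, log-rank test, 35 per arm, 20,000 runs per scenario.

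- All dosed patients: 5.1% to 6.0% in every scenario.
- Completers only (T3 at most 240 min), duration doubled:

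| Control T3 median | ρ = 0.3 | ρ = 0.5 | ρ = 0.7 |
|---|---|---|---|
| 60 min | 6.3% | 7.0% | 8.0% |
| 120 min | 6.4% | 9.6% | 15.9% |

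If the four-hour removal after open-label morphine is applied as well, the rows become 6.1/6.5/7.6% and 6.5/8.0/12.9%. The mean T1 difference, combination minus morphine, is −1.7 to −7.0 min. With duration ×1.5, rejection is 5.3% to 7.9%. With ρ = 0 it is 5.2% to 5.6%.

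**5. The corrected interval T3, and why its four-hour rule matters.** This supports the fix; it does not measure the definition error. With exponential times, the share with no third request by 240 min is exp(−240 ln 2 / median), and 35 completers require 35/(1 − share) dosed patients.

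| Control median (min) | 30 | 60 | 90 | 120 |
|---|---|---|---|---|
| Share, morphine | 0.004 | 0.062 | 0.157 | 0.250 |
| Share, duration doubled | 0.062 | 0.250 | 0.397 | 0.500 |
| Dosed for 35 completers, morphine | 35 | 37 | 42 | 47 |
| Dosed for 35 completers, combination | 37 | 47 | 58 | 70 |
| Power, 35 dosed per arm, kept and censored | 80% | 75% | 69% | 62% |
| Power, 35 completers per arm, removed excluded | 65% | 31% | 18% | 13% |

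The power rows are for duration doubled (log-rank, 10,000 runs). With duration ×1.5 they become 39/35/32/29% against 32/17/11/9%.

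**The case against.** The timing error is plain from the text and needs no simulation. The arguments on the other side concern scope and size.

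- **The selection figures rest on assumptions.** The documents give no correlation, medians or effect on duration, and they do not say that removed patients' data are discarded. The low end, just over 6%, hardly exceeds the 5.1% to 6.0% seen with all dosed patients. The top, 15.9%, is one corner: control median 120 min, duration doubled, correlation 0.7. At median 60 min the figure does not exceed 8.0%. This stands, so the figures show a possible distortion and are not a forecast.
- **The power comparison is not like for like.** It sets 35 dosed per arm against 35 completers per arm, who require more dosed patients. The plan counts completers: "We are planning for 70 patients to complete the study, 35 in each group" (Section 1.0), and "with 35 patients completing the study per arm" (Section 14.0). If everyone dosed to reach 35 completers is kept and censored, power is about 81% to 83% with duration doubled and 38% to 40% with ×1.5. This is correct, and it means the table understates the benefit of keeping these patients.
- **Part of the remedy is already there.** Section 14.0 uses T1 to stratify, and the primary area B already reflects duration. Both are true. The first confirms that T1 belongs at baseline. The second limits the loss, but area B mixes the degree of relief with its length and does not replace a time outcome.

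**Conclusion.** The concern holds and is worth fixing. As defined, time-to-first-rescue is a pretreatment variable. That follows from the order of events alone, needs no assumption, and is contradicted nowhere in the plan.

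The loss is one secondary estimate, the duration of analgesia. The primary B/A comparison and its 80% power are untouched. The risk of a spurious result is conditional: about 5% to 6% rejection with all dosed patients, and about 6% to 16% with completers only, a doubled duration and correlations of 0.3 to 0.7. Confidence is high for the timing and lower for these simulated ranges. Even the corrected outcome would be weak for a 1.5-fold effect, with power of about 29% to 40% when all dosed patients are kept.

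**What to change.** In Section 14.0:

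1. Define the secondary time outcome as the interval from the second request (study drug administration) to the third request.
2. State that this analysis includes every patient who received study drug, that those with no third request by four hours are censored at 240 minutes, and that the method handles censoring (log-rank or Cox, for example).
3. Keep PCA stop to first request only as a baseline covariate or stratifier, and remove it from the outcomes.

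Point 2 concerns which data are kept for analysis; it changes no dose, timing or clinical rule. Section 9.0 both completes and removes the four-hour patient, and Sections 4.2 and 13.0 have removal. These passages must be reconciled, with a cross-reference to the analysis rule.

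The cost is about two sentences in Section 14.0, for the interval and for retention with censoring, the deletion of the old interval from the outcomes, and short cross-references in Sections 4.2, 9.0 and 13.0. No new data are needed, because Form 2 records the times of the second and third requests. It has no separate field for study drug administration time, but Section 14.0 already treats the second request and administration as the same time zero.
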